6.10.1.29 Calibration stability

To demonstrate performance of the system spanning the duration between calibration points, the Sensor performance will be assessed using Agreement in 4-hour increments over the period from 0 to 12 hours (Table 25 in APPENDIX 1).

The example tables that compare the effectiveness endpoints calculated for the three different combinations of 2 generations of hardware and 2 generations of firmware are shown in Appendix 2.

7 References and Supporting Documentation

5. Clinical and Laboratory Standards Institute. Performance Metrics for Continuous Interstitial Glucose Monitoring: Approved Guideline. CLSI Document POCT05-A. Wayne, PA. 2008.
6. In-vitro Diagnostic Test Systems-Requirements for Blood Glucose Monitoring Systems for Self Testing in Managing Diabetes Mellitus. ISO 15197:2003. Geneva.

7. U.S. Food and Drug Administration. The Content of Investigational Device Exemption (IDE) and Premarket Approval (PMA) Applications for Low Glucose Suspend (LGS) Device Systems. Draft Guidance. 2011.
8. U.S. Food and Drug Administration. The Content of Investigational Device Exemption (IDE) and Premarket Approval (PMA) Applications for Artificial Pancreas Device Systems. Draft Guidance. 2011.
9. U.S. Food and Drug Administration. Design Considerations for Pivotal Clinical Investigations for Medical Devices. 2013.
10. Clinical investigation of medical devices for human subjects — Good clinical practice. ISO 14155:2011. Geneva.

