4.4 Sensor Accuracy (Sampling) Visit 3 – Day 1 (\pm 0 Days)

Approximate visit duration - 19 hours

Approximate sampling duration – 16 hours

Approximate visit timeline:

Approximate time	Activity	~Time relative to first IV sample
~16:00	Admission and First Calibration	T=0 -2:00
~16:30	Blood draw for dexamethasone	T=0 -1:30
~17:00	Fingerstick	T=0 -1:00
~17:15-17:45	Period for glucose stabilization	T=0 -0:45 - -0:15
~18:00	First IV blood sample drawn/ second calibration	T=0 0:00
~18:00 – 0:00	For qualifying subjects, hyperglycemia challenge to achieve hyperglycemia to goal glucose >350 mg/dL. 
 Sampling @ 5 min when glucose ≥ 325 mg/dL, with a target duration of 1 hour. Challenge may be stopped once 12 samples ≥325 mg/dL are collected. 	T=0 0:00 – +6:00
19:00	Fingerstick	T=0 0:00 - +1:00
~20:00	Third calibration	T=0 0:00 - +2:00
21:00	Fingerstick	T=0 0:00 - +3:00
~22:00	Fourth calibration	T=0 0:00 - +4:00
~23:00	Fingerstick	T=0 0:00 - +5:00
~0:00	Fingerstick	T=0 0:00 - +6:00
~0:00-07:00	Overnight period 
 Overnight period. Sampling q 15 min when glucose is > 75 mg/dL and < 325 mg/dL. Q 5 minutes when outside this range. 	T=0 +6:00 - +13:00
~07:00	CGM system calibration	T=0 +13:00

Approximate time	Activity	~Time relative to first IV sample
~07:00-10:00	
For qualifying subjects, hypoglycemia challenge to achieve hypoglycemia target <60 mg/dL.
 
 Sampling q 5 min when glucose ≤ 75mg/dL. Target 24 YSI values <75 mg/dL, including 6 YSI values <60 mg/dL at q 5 min before rescue. Subjects fed low glycemic morning meal and YSI data collection discontinued once challenge is concluded. Hourly fingersticks from 07:00 to 11:00. 	T=0 +13:00 - +16:00
~08:00	Fingerstick	T=0 +13:00 - +14:00
~09:00	Fingerstick	T=0 +13:00 - +15:00
~10:00	Fingerstick	T=0 +13:00 - +16:00
~10:00-11:00	Discharge preparation	T=0 +16:00 - +17:00
~10:30	Blood draw for dexamethasone	T=0 +16:30
~11:00	Discharge	T=0 +17:00

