4.5 Sensor Accuracy (Sampling) Overnight Visits

Visit 4 – Day 7 Accuracy (Sampling) Visit (± 1 Day)

Visit 5 – Day 14 Accuracy (Sampling) Visit (± 1 Day)

Approximate visit duration – 18 hours

Approximate sampling duration – 16 hours

Approximate visit timeline:

Approximate time	Activity	Time relative to first IV sample
~17:00	Admission	T=0 -1:00
~17:15-17:45	Period for glucose stabilization and CGM calibration	T=0 -0:45 - -0:15
~17:30	Blood draw for dexamethasone, prior to YSI sampling	
~18:00	First IV blood sample drawn	T=0 0:00
~18:00 – 0:00	
For qualifying subjects, hyperglycemia challenge to achieve hyperglycemia to goal glucose >350 mg/dL.Sampling @ 5 min when glucose \geq 325 mg/dL, with a target duration of 1 hour.
Challenge may be stopped once 12 samples \geq325 mg/dL are collected.	T=0 0:00 – +6:00
~19:00	Fingerstick blood glucose	T=0 +1:00
~20:00	Fingerstick blood glucose	T=0 +2:00
~21:00	Fingerstick blood glucose	T=0 +3:00

Approximate time	Activity	Time relative to first IV sample
~22:00	Fingerstick blood glucose	T=0 +4:00
~23:00	Fingerstick blood glucose	T=0 +5:00
~0:00	Fingerstick blood glucose	T=0 +6:00
~0:00-07:00	
 Overnight period. Sampling q 15 min when glucose is > 75 mg/dL and < 325 mg/dL. Q 5 minutes when outside this range. 	T=0 +6:00 - +13:00
~07:00	Fingerstick blood glucose and sensor calibration	T=0 +13:00
~07:00-10:00	
For qualifying subjects, hypoglycemia challenge to achieve hypoglycemia target <60 mg/dL.
 
 Sampling q 5 min when glucose ≤ 75 mg/dL. Target 24 YSI values <75 mg/dL including 6 YSI values <60 mg/dL at q 5 min before rescue. 
Subjects fed low glycemic morning meal and YSI data collection discontinued once challenge is concluded.
	T=0 +13:00 - +16:00
~08:00	Fingerstick blood glucose	T=0 +14:00
~09:00	Fingerstick blood glucose	T=0 +15:00
~10:00	Fingerstick blood glucose	T=0 +16:00
~10:00-11:00	discharge preparation	T=0 +16:00 - +17:00
~10:30	Blood draw for dexamethasone after YSI sampling complete.	T=0 +16:30
~11:00	Discharge	T=0 +17:00

The following procedures/instructions will be followed for accuracy (sampling) visits at Visits 4 and 5:

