4.5.13 Calibration (Visits 4 & 5)

Subjects/clinicians will calibrate the system during the time period for glucose stabilization and will calibrate again approximately 12 hours later. The morning calibration reminder, adjusted through use of the HHD and mobile medical application will be set to approximately 12 hours after the evening calibration entry.

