4.6 Sensor Accuracy (Sampling) Daytime Visits

Visit 6 – Day 30 Accuracy (Sampling) Visit (± 7 Days)

Visit 7 – Day 60 Accuracy (Sampling) Visit (± 7 Days)

Visit 8 – Day 90 Accuracy (Sampling) Visit (-3/+7 Days)

	Approximate Visit	Approximate Sampling
Visit 6 (Day 30 ± 7 Days)	14 hours	12.5 hours
Visit 7 (Day 60 ± 7 Days)	14 hours	12.5 hours

Visit 8 (Day 90 -3/+7 Days)	15 hours	12.5 hours
-----------------------------	----------	------------

Approximate visit timeline:

Approximate time	Activity	Time relative to first IV sample
~07:00	Admission	T=0 -1:00
~07:15-07:45	Period for glucose stabilization and CGM calibration	T=0 -0:45 - -0:15
~08:00	First IV blood sample drawn	T=0 0:00
~08:00 – 13:00	
For qualifying subjects, hypoglycemia challenge to achieve hypoglycemia target <60 mg/dL.
 
 Sampling q 5 min when glucose \leq 75 mg/dL. Target 24 YSI values <75 mg/dL including 6 YSI values <60 mg/dL at q 5 min before rescue. Subjects fed low glycemic meal. 	T=0 0:00 – +5:00
~08:00 – 13:00	
 Alternatively, for qualifying subjects, hyperglycemia challenge to achieve hyperglycemia to goal glucose >350 mg/dL. Sampling @ 5 min when glucose \geq 325 mg/dL, with a target duration of 1 hour. Challenge may be stopped once 12 samples ≥ 325 mg/dL are collected. 	T=0 0:00 – +5:00
~08:00 – 13:00	For those subjects not following a basal/bolus routine on MDI or CSII, glucose control will be free range.	T=0 0:00 – +5:00
~09:00	Fingerstick blood glucose	T=0 +1:00
~10:00	Fingerstick blood glucose	T=0 +2:00
~11:00	Fingerstick blood glucose	T=0 +3:00
~12:00	Fingerstick blood glucose	T=0 +4:00
~13:00	Fingerstick blood glucose	T=0 +5:00
~13:00-16:00	Recovery Period with meal/bolus and glucose stabilization	T=0 +5:00 - +8:00
~16:00-19:30	Free range glucose control	T=0 +8:00 - +11:30
~14:00	Fingerstick blood glucose	T=0 +6:00
~15:00	Fingerstick blood glucose	T=0 +7:00

Approximate time	Activity	Time relative to first IV sample
~16:00	Fingerstick blood glucose	T=0 +8:00
~17:00	Fingerstick blood glucose	T=0 +9:00
~18:00	Fingerstick blood glucose	T=0 +10:00
~19:00	Fingerstick blood glucose	T=0 +11:00
~19:30-20:30	Discharge preparation period	T=0 +11:30 - +12:30
~20:00	Blood draw for dexamethasone	T=0 +12:00
~20:30	Last IV blood sample drawn	T =0 + 12:30
21:00	Discharge	T=0 +13:00

The following procedures/instructions will be followed for accuracy (sampling) daytime visits at days 30, 60 and 90:

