6.10 Exploratory Effectiveness Endpoint

Exploratory effectiveness measures are discussed in this section. Only descriptive statistics will be provided for these exploratory outcomes. All analyses will be provided as described below and by clinic visit day. SMBG glucose values may also be used as reference for some of these analyses.

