Time from Calibration	Number of Paired Senseonics CGM and Reference	Percent within 20/20% Reference	Percent within 30/30% Reference	Percent within 40/40% Reference
0-4 hours				
4-8 hours				
8-12 hours				

APPENDIX 2: EXAMPLE FIGURES AND TABLES OF STATISTICAL ANALYSIS RESULTS FOR THE DIFFERENT HARDWARE AND FIRMWARE COMBINATIONS

Table 2.1. Investigational Transmitter Deficiencies (Sample Table)

Type of Transmitter Deficiency	Gen 1 Tx		Gen 2 Tx	
	Number Reported	% of Total	Number Reported	% of Total
Package Label	TBD	TBD	TBD	TBD
Product Defect	TBD	TBD	TBD	TBD
Damaged Package	TBD	TBD	TBD	TBD
Product Safety	TBD	TBD	TBD	TBD
Product Performance	TBD	TBD	TBD	TBD
Other	TBD	TBD	TBD	TBD

Table 2.2. CGM System Difference to YSI within YSI Glucose Range (Sample Table)

CGM System Difference to YSI within YSI Glucose Range				
YSI Glucose Range (mg/dL)	Number of Points	Hardware Version (Firmware Version)		
		Gen 1 Tx (Study FW)	Gen 2 Tx (Study FW)	Gen 2 Tx (Updated FW)
Mean Relative Difference (%)				
Overall	TBD	TBD	TBD	TBD
<40*	TBD	TBD	TBD	TBD
40-60*	TBD	TBD	TBD	TBD
61-80*	TBD	TBD	TBD	TBD
81-180	TBD	TBD	TBD	TBD
181-300	TBD	TBD	TBD	TBD
301-350	TBD	TBD	TBD	TBD
351-400	TBD	TBD	TBD	TBD
>400	TBD	TBD	TBD	TBD
Median Relative Difference (%)				
Overall	TBD	TBD	TBD	TBD
<40*	TBD	TBD	TBD	TBD
40-60*	TBD	TBD	TBD	TBD
61-80*	TBD	TBD	TBD	TBD
81-180	TBD	TBD	TBD	TBD
181-300	TBD	TBD	TBD	TBD
301-350	TBD	TBD	TBD	TBD
351-400	TBD	TBD	TBD	TBD
>400	TBD	TBD	TBD	TBD
Mean Absolute Relative Difference (%)				
Overall	TBD	TBD	TBD	TBD
<40*	TBD	TBD	TBD	TBD
40-60*	TBD	TBD	TBD	TBD

CGM System Difference to YSI within YSI Glucose Range				
YSI Glucose Range (mg/dL)	Number of Points	Hardware Version (Firmware Version)		
		Gen 1 Tx (Study FW)	Gen 2 Tx (Study FW)	Gen 2 Tx (Updated FW)
61-80*	TBD	TBD	TBD	TBD
81-180	TBD	TBD	TBD	TBD
181-300	TBD	TBD	TBD	TBD
301-350	TBD	TBD	TBD	TBD
351-400	TBD	TBD	TBD	TBD
>400	TBD	TBD	TBD	TBD
Median Absolute Relative Difference (%)				
Overall	TBD	TBD	TBD	TBD
<40*	TBD	TBD	TBD	TBD
40-60*	TBD	TBD	TBD	TBD
61-80*	TBD	TBD	TBD	TBD
81-180	TBD	TBD	TBD	TBD
181-300	TBD	TBD	TBD	TBD
301-350	TBD	TBD	TBD	TBD
351-400	TBD	TBD	TBD	TBD
>400	TBD	TBD	TBD	TBD

*For YSI ≤80 mg/dl, the differences in mg/dl are included instead of percent difference (%).

Table 2.3. CGM System Difference to YSI within CGM System Glucose Range (Sample Table)

CGM System Difference to YSI within CGM System Glucose Range				
CGM Glucose Range (mg/dL)	Number of Points	Hardware Version (Firmware Version)		

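### Table 25 confounds time since calibration with glucose phase, so it cannot show whether calibration holds; the direction of the error is unknown

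*SAP*

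**What the plan says.** The calibration-stability analysis is meant to show how the system performs across the gap between calibrations. The method is one sentence: "the Sensor performance will be assessed using Agreement in 4-hour increments over the period from 0 to 12 hours" (SAP 6.10.1.29). Table 25 in SAP Appendix 1 has rows headed "Time from Calibration" (0-4, 4-8 and 8-12 hours). Its columns are the number of pairs and the percent within 20/20, 30/30 and 40/40. SAP 6.10 adds a display by visit: "All analyses will be provided as described below and by clinic visit day".

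The protocol fixes when calibrations and challenges occur:

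- **Visit 3 (4.4):** evening calibrations at about 16:00, 18:00, 20:00 and 22:00, then "CGM system calibration" at about 07:00. The hypoglycemia challenge runs 07:00-10:00.
- **Visits 4 and 5 (4.5):** calibration at about 17:15-17:45, hyperglycemia challenge 18:00-0:00, overnight 0:00-07:00. At about 07:00 comes "Fingerstick blood glucose and sensor calibration", and 07:00-10:00 is given as "For qualifying subjects, hypoglycemia challenge to achieve hypoglycemia target <60 mg/dL". Section 4.5.13 instead says that subjects or clinicians "will calibrate again approximately 12 hours later" than the evening calibration.
- **Visits 6-8 (4.6):** "Period for glucose stabilization and CGM calibration" at about 07:15-07:45, one challenge 08:00-13:00, recovery 13:00-16:00, free range 16:00-19:30. The next calibration is about 12 hours after the first (4.6.12).

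**The concern.** A comparison across time-since-calibration rows is informative only if the rows contain similar glucose conditions. Here the timetable itself puts different conditions in different rows. The SAP already treats glucose range (6.10.1.3), rate of change (6.10.1.25) and night versus day (6.10.1.7) as factors that may affect accuracy, but tabulates each alone. None is crossed with time since calibration. The by-visit display does not help, because the link arises within each visit.

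At stake is the reading of Table 25. Any difference between rows, or its absence, could come from glucose phase rather than from ageing of the calibration. The system is also intended to alert for low glucose, yet no induced hypoglycemia is scheduled 8-12 hours after a calibration, and the table would not reveal that gap.

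**Working it through.** **1. The plan's own sample counts.** The Schedule of Events gives 89 samples at Visits 3-5 and 59 at Visits 6-8. Check: 13 × 4 + 3 × 12 = 88, plus the first sample = 89; 11.5 × 4 + 1 × 12 = 58, plus the first = 59. Both reproduce.

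**2. Hours since calibration, from the timetables.**

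| Visits | Calibration | Phase (clock time) | Hours since calibration |
|---|---|---|---|
| 3 | 22:00 | overnight, 0:00-07:00 | 2-9 |
| 3, 4, 5 | 07:00 | hypoglycemia challenge, 07:00-10:00 | 0-3 |
| 4, 5 | 17:15-17:45 | hyperglycemia challenge, 18:00-0:00 | 0.25-6.75 |
| 4, 5 | 17:15-17:45 | overnight, 0:00-07:00 | 6.25-13.75 |
| 6-8 | 07:15-07:45 | challenge, 08:00-13:00 | 0.25-5.75 |
| 6-8 | 07:15-07:45 | free range, 16:00-19:30 | 8.25-12.25 |

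**3. Scheduled YSI samples per qualifying subject, by Table 25 row.** Calibration is taken at the middle of its window (17:30 or 07:30). Sampling is every 15 minutes, and every 5 minutes in the challenge target blocks. Assumed block times:

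- Visits 3-5: hypoglycemia 08:00-10:00; hyperglycemia hour starting at 20:00, 21:30 or 22:30.
- Visits 6-8: hypoglycemia 09:00-11:00 or 11:00-13:00; the hyperglycemia hour within 0-4 h.

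| Visit | 0-4 h | 4-8 h | 8-12 h | Over 12 h |
|---|---|---|---|---|
| 3 | 69 (8 overnight) | 16, all overnight | 4, all overnight | 0 |
| 4, 5; second calibration 07:00 | 43-51, all in challenge windows | 16-24 (6 overnight) | 17, all overnight | 5, all overnight |
| 4, 5; second calibration about 05:30 | 42-50 (6 overnight) | 23-31 (6 overnight) | 16, all overnight | 0 |
| 6-8, hypoglycemia | 23-35 (5 free range) | 16-28 | 16 (14 free range, 2 recovery) | 0 |
| 6-8, hyperglycemia | 27 (5 free range) | 16 | 16 (14 free range, 2 recovery) | 0 |

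The hypoglycemia rows for Visits 6-8 total 67 rather than 59, because the target is 24 five-minute samples rather than one hour of them.

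The 24 hypoglycemia-target samples fall as follows:

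- Visit 3: all in 0-4 h.
- Visits 4 and 5 with the 07:00 calibration: all in 0-4 h, where they make up 24/51 = 47% to 24/43 = 56% of the row. With calibration at about 05:30: 18 in 0-4 h and 6 in 4-8 h.
- Visits 6-8: 6 to 24 in 0-4 h, the rest in 4-8 h.
- 8-12 h: none, at any visit, under any of these layouts.

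**4. Which way the table errs.** The documents give no agreement rates by phase, so this step is illustrative. Let c be agreement in challenge-target pairs and q agreement in all other pairs. Let w be the challenge-target share of the 0-4 h row and k any overnight loss from compression. Assume a true 5-point fall from 0-4 h to 8-12 h.

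The 0-4 h row shows w·c + (1 − w)·q, and the 8-12 h row shows q − 5 − k. So the crude fall = 5 + k − w(q − c).

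For Visits 4 and 5, w runs from 24/43 = 0.56 to 36/51 = 0.71 (the latter when the hyperglycemia hour also falls in 0-4 h). With q = 90%:

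| c | k | Crude result, true fall 5 |
|---|---|---|
| 80% | 0 | rise of 0.6 to 2.1 |
| 85% | 0 | fall of 1.5 to 2.2 |
| 90% | 0 | fall of 5.0 |
| 95% | 0 | fall of 7.8 to 8.5 |
| 85% | 5 | fall of 6.5 to 7.2 |
| 90% | 5 | fall of 10.0 |

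The sign of the error depends on c and k, which are unknown.

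**5. Why c could exceed q.** At or below 80 mg/dL, agreement uses an absolute limit (SAP 6.10.1.2). A 20 mg/dL limit is 20/60 = 33% at 60 mg/dL and 20/75 = 27% at 75 mg/dL, against 20% above 80. With equal, centered normal relative error (assumed SD 12%), 20/20 agreement is 99.5% at 60 mg/dL and 90.4% above 80. Challenge lows reduce 0-4 h agreement only if their relative error exceeds that elsewhere by about 27/20 = 1.3 times (at 75) to 33/20 = 1.7 times (at 60).

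**The case against.** A reader might infer that the timetable hides drift: difficult challenge pairs depress the early row, easy pairs lift the late one, and agreement looks stable while the sensor drifts. The documents do not support that direction. It needs worse agreement in challenges than later, and no figure is given. The wider tolerance at low glucose can raise early agreement. At Visits 4 and 5 the late row is overnight, when SAP 6.10.1.7 says that compression may occur, which would exaggerate drift. Nor do the documents show that late glucose is quiet, since free range is uncontrolled.

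It would also be too strong to say that nearly all induced hypoglycemia sits in 0-4 h. That holds for Visits 3-5 on the timetable. It need not hold at Visits 6-8, or if the second calibration at Visits 4 and 5 comes about 12 hours after the first.

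Other points limit the concern. Observation subjects and those not on a basal/bolus routine contribute free-range pairs, in unstated numbers. SAP 6.10 allows SMBG as a reference for some analyses, which could add home pairs, but does not say so for Table 25; the counts above assume YSI. The analysis is exploratory and descriptive, with no acceptance criterion.

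These points remove any claim about direction and limit the weight of the concern. They do not make the rows comparable.

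**Conclusion.** The concern holds as confounding of unknown direction. For scheduled YSI samples of qualifying subjects, no challenge sample falls at 8-12 hours, and that row is entirely overnight (Visits 3-5) or almost entirely free range (14 of 16 at Visits 6-8). Table 25 as laid out therefore cannot separate calibration drift from glucose level, rate of change or night/day.

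The size of the bias cannot be derived from the documents. The spread from a 2.1-point rise to a 10.0-point fall, against a true 5-point fall, rests on assumed agreement rates and shows only that the sign is open. The clock intervals rest on the approximate times in the timetables; the row counts also rest on the assumed challenge placement.

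The point affects one exploratory table and leaves the MARD endpoint untouched. It is worth correcting before results are seen, so that the split is not chosen afterwards.

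**What to change.** In SAP 6.10.1.29:

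- Present Table 25 within YSI range (≤80, 81-180, >180 mg/dL) and within the rate-of-change categories already in Table 21. Show night/day for Visits 4 and 5.
- Read stability from within-stratum comparisons, mainly 81-180 mg/dL with system rate of change in [-1,1]. Do not exclude challenge windows by clock time: that would nearly empty the 0-4 h row for qualifying subjects at Visits 4-8 and leave mostly Visit 3 or non-challenge subjects as the early comparison.
- Print the number of pairs in every cell. Make no low-glucose stability claim for time rows with few or no pairs at ≤80 mg/dL.

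In the protocol, reconcile the second calibration at Visits 4 and 5. The 4.5 timetable puts it at 07:00 (13.5 hours after 17:30), and 4.5.13 about 12 hours after the first. The choice decides which row some pairs enter. On the timetable, about 5 samples per visit fall beyond 12 hours and outside Table 25 altogether.

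The cost is smaller cells in a descriptive table; the data and rate categories are already planned. Two limits remain. At Visits 4 and 5 the 8-12 h row is all night, so a daytime contrast must come from Visits 6-8. The system's rate of change is itself a sensor output, so sensor error can move a pair between categories.

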1.1.2 Calibration

The primary Senseonics CGM System will be calibrated by the Subjects according to the Eversense CGM User Guide, using the study-provided, commercially available BG Meter (Subject SMBG Meter), according to the SMBG meter manufacturer instructions. The

calibration process automatically moves through three phases: Warm Up, Initialization, and Daily Calibration:

- Warm Up is the first 24 hours after Sensor insertion. During this period, Glucose information is not calculated. No calibration is performed.
- Initialization can be performed a minimum of 24 hours after Sensor insertion. Following the Warm Up phase, the entering of four successful calibration BG readings within 24 hours is required for successful completion of Initialization. Glucose information will begin to be calculated after the second calibration is entered successfully.
- Daily Calibration requires 2 successful calibrations per day, a minimum of 10 and maximum of 14 hours apart.

If the Subject fails to wear the Transmitter for more than 24 hours, or is unable to enter a successful calibration, then glucose information will not be calculated and the Subject will re-enter the Initialization phase.

The secondary Senseonics CGM System will not require calibration and will have the ability to collect and log data only, and it will not calculate or store glucose information.

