6.3 Data for Analysis

All data will be used for the study safety and effectiveness analysis.

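### The calibration-stability table stops 12 h after calibration, but the protocol permits 14 h and the Visit 4 and 5 timetable, if followed, reaches 13.25 to 13.75 h

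*SAP*

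**What the plan says.** SAP 6.10.1.29 gives its aim as "To demonstrate performance of the system spanning the duration between calibration points". It then fixes the scope: "the Sensor performance will be assessed using Agreement in 4-hour increments over the period from 0 to 12 hours". Table 25 in SAP Appendix 1 follows this with three rows: 0-4, 4-8 and 8-12 hours.

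The permitted interval is longer. Protocol 1.1.2 states: "Daily Calibration requires 2 successful calibrations per day, a minimum of 10 and maximum of 14 hours apart".

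For Visits 4 and 5 the protocol gives two accounts of the in-clinic interval:

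- The timetable in Protocol 4.5 has "Period for glucose stabilization and CGM calibration" at about 17:15-17:45. The next calibration it lists is "Fingerstick blood glucose and sensor calibration" at about 07:00. Between midnight and 07:00 the reference schedule is "Sampling q 15 min when glucose is > 75 mg/dL and < 325 mg/dL", and every 5 minutes outside that range.
- Protocol 4.5.13 says that subjects or clinicians "will calibrate again approximately 12 hours later" and sets the app reminder to match. Protocol 5.5.2 says the same for in-clinic sessions generally.

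**The concern.** A calibration-stability table is there to show whether agreement worsens as the calibration ages, so the pairs on the oldest calibration are the ones it most needs. Ending at 12 h leaves the last 2 h of the permitted interval undescribed, whatever happens at a given visit. The study's own timetable, taken at face value, also produces reference samples in that window at two of the six accuracy visits. Table 25 is the only output visible in the plan that is organised by time from calibration, so these pairs are not described by calibration age anywhere else.

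**Working it through.** **Check of the sampling rates.** Protocol section 4 plans 13 h at 4 samples per hour and 3 h at 12 per hour for a 16 h session: 13 × 4 + 3 × 12 = 88, or 89 with the first sample. This reproduces the protocol's approximate figure of 89 per session at Visits 4 and 5.

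**Planned gap by the timetable.** From 17:15 to 07:00 is 13.75 h; from 17:45 to 07:00 is 13.25 h.

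**Samples more than 12 h after calibration.** These are points on the 15-minute grid later than the evening calibration plus 12 h, up to 07:00. A sample at exactly 12 h is left in the 8-12 h row.

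| Evening calibration | 12 h mark | Gap to 07:00 | Samples beyond 12 h, 07:00 included | 07:00 excluded |
|---|---|---|---|---|
| 17:15 | 05:15 | 13.75 h | 7 (05:30 to 07:00) | 6 |
| 17:30 | 05:30 | 13.50 h | 6 (05:45 to 07:00) | 5 |
| 17:45 | 05:45 | 13.25 h | 5 (06:00 to 07:00) | 4 |

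The 07:00 sample is doubtful. SAP 6.4 pairs it with the first sensor reading up to 5 minutes later, which may come after the 07:00 calibration. The count is therefore 4 to 6 without it and 5 to 7 with it.

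**Share of the session.** 4/89 = 4.5% and 7/89 = 7.9%.

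**Over both visits.** If all 36 inserted subjects attend both: 4 × 36 × 2 = 288 to 7 × 36 × 2 = 504 reference samples.

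**Sensitivity to the actual gap** (15-minute sampling, with the sample at the moment of recalibration counted):

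| Gap between calibrations | Samples beyond 12 h |
|---|---|
| 12 h | 0 |
| 12.5 h | 2 |
| 13 h | 4 |
| 14 h | 8 |

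If glucose were at or below 75 mg/dL or at or above 325 mg/dL throughout that window, 5-minute sampling would give 15 to 21 samples instead of 5 to 7.

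**Other visits.** At Visit 3 the last evening calibration is at about 22:00 and the next at about 07:00, a gap of 9 h, so nothing is lost. At Visits 6 to 8 the timetable lists no evening calibration, but Protocol 4.6.12 asks for a repeat at about 12 h. Done at 12 h (about 19:15-19:45), it leaves no sample uncovered. If it comes only after the last sample at about 20:30, that sample is 12.75 to 13.25 h old and 3 to 5 samples per visit lie beyond 12 h (20:30 − 19:45 = 0.75 h × 4 = 3; 20:30 − 19:15 = 1.25 h × 4 = 5).

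**The case against.** The strongest objection is that 12 h is the protocol's nominal interval. Protocol 4.2.6, 4.5.13, 4.6.12 and 5.5.2 all say about 12 h, 14 h is only the outer limit, and every timetable entry is marked approximate. On that reading the Visit 4 and 5 count is zero. This stands, and it makes the count conditional. It does not remove the point. A repeat at 12 h would fall at about 05:15-05:45, where the timetable lists neither a calibration nor a fingerstick, and Protocol 4.5.10 exempts the overnight period from hourly fingersticks. The mismatch with the 14 h limit remains in any case.

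Three stronger readings are tempting, and the documents do not support them.

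- A reader might infer a conflict with SAP 6.3, which says "All data will be used for the study safety and effectiveness analysis". That sentence does not require every pair to appear in every table. Other planned outputs are also subsets, such as the mean absolute difference at reference values of 80 mg/dL or less.
- A reader might infer that late pairs would be put in the 8-12 h row and make its label untrue. Nothing in the SAP suggests this; the stated scope simply leaves them out.
- A reader might infer that the missing row is what prevents calibration age from being separated from night-time in Tables 10A and 10B. By the timetable, samples from midnight to 07:00 are 6.25 to 13.75 h old, so age and night do run together. But at Visits 4 and 5 a row beyond 12 h would consist of night samples only, with no daytime counterpart, and could not separate them.

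**Conclusion.** The point holds in a limited form. Table 25 does not cover the interval that SAP 6.10.1.29 says it is meant to show, because it ends 2 h short of the permitted maximum. Under the Visit 4 and 5 timetable, about 4 to 7 reference samples per session (roughly 4.5% to 8% of about 89) have no row. With a repeat calibration at 12 h, none are affected. The range assumes 15-minute overnight sampling, an evening calibration between 17:15 and 17:45, and no calibration before 07:00.

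Table 25 is exploratory and descriptive. The pairs remain in MARD and in the other accuracy tables, so no effectiveness result changes. The documents give no basis for saying that accuracy drifts after 12 h; the point is only that the table could not show it.

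**What to change.** In SAP 6.10.1.29, raise the upper limit from 12 to 14 hours. Add a row for more than 12 to 14 hours to Table 25 and to the by-visit versions that SAP 6.10 already provides for. State under the table how many pairs, if any, lie beyond 14 h.

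Define the time origin as well. For the primary (Gen 1) system, use time since the last calibration it accepted. That definition fails for Gen 2: Protocol 4.2.6 has calibrations entered into the Gen 1 transmitter only, and Protocol 1.1.2 says the secondary system needs none, yet SAP 4.2.3 asks for the exploratory endpoints in two Gen 2 configurations. For those, use time since the last calibration value that entered the calculation of that sensor's glucose.

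The cost is a few words and one row. Sensor readings are timestamped (Protocol 10.2.1) and transmitter data are already uploaded to monitor calibration compliance (Protocol 10.2.2), so no new data are needed. The change works whichever protocol text the sites follow.

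The downside is that the new row will be small and will come almost entirely from the nights of Visits 4 and 5. It must be read with its count, and it should not be used to separate calibration age from night-time effects.
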